## 6.2. **Pazopanib**

### 6.2.1. **Dose Levels for Pazopanib**

Pazopanib starting dose may be at either 400 or 800 mg daily. Pazopanib decrease should be in 200-mg steps, for pazopanib-related AEs that require dose reductions (Section 6.2.2).

Pazopanib dosing may not be reduced below 200 mg daily. Subjects requiring a dose reduction below 200 mg daily should discontinue pazopanib therapy. Pazopanib dosing may not be increased above 800 mg daily. Dose modification algorithms for specific toxicities are detailed below in Section 6.2.2. For all other Grade 3 or 4 non-hematologic toxicities (except alopecia, nausea, or vomiting) that are at least in part attributable to the study drug, the dose should be held until the toxicity resolves to ≤ Grade 1. Treatment should then be resumed at a reduction of one dose level. For recurrent grade 3 or 4 toxicity, the study drug should again be held until the toxicity resolves to ≤ Grade 1 and then reintroduced at another dose level reduction. If the toxicity has abated with reduction of the dose and dose re-escalation is considered safe by the investigator, the study drug dose can then be increased step-wise back to the pre-event dose (in 200 mg increments, after monitoring for 14 days at each dose level to ensure that toxicity did not recur or worsen).

Pazopanib is absorbed orally, with median time to achieve peak concentrations of 2 to 4 hours after the dose. If a dose is missed, it should not be taken if it is less than 12 hours until next dose. For pazopanib dose reduction and stopping rules, please refer to Table 10 and Table 11.

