### 6.2.2. **Pazopanib Dose Modification and Stopping Rules**

Pazopanib is dosed continuously. Modifications to pazopanib dosing should follow the table below. Additional dose reductions may be made outside of the defined parameters below, at

investigator discretion. Dose levels may not be re-escalated outside of the defined guidelines. All dose reductions or re-escalations must be made in 200 mg increments, unless otherwise specified.

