	ALT, AST, or Bilirubin Elevation	Grade 2	
Nab-Sirolimus: See Section 6.1.3.1 and 6.1.3.2.
 
Subjects with ALT/AST > 3 x ULN, or Total Bilirubin > 3 x ULN, or Alk Phos > 8 x ULN are recommended for withholding of nab-Sirolimus.
 
Pazopanib: Continue pazopanib, but monitor weekly until ALT, AST, and bilirubin return to ≤ grade 1.

		Grade 3-4	
Nab-Sirolimus: See Section 6.1.3.1 and 6.1.3.2.
 
Subjects with ALT/AST > 3 x ULN, or Total Bilirubin > 3 x ULN, or Alk Phos > 8 x ULN are recommended for withholding of nab-Sirolimus.
 
Pazopanib: Delay pazopanib until improved to ≤ grade 1. Restart treatment with one dose level reduction of pazopanib.

	ALT/AST and Bilirubin (Grade 2 or greater ALT/AST elevation with concurrent Grade 2 or greater bilirubin elevation)	Grade 2+	
Nab-Sirolimus: Discontinue nab-Sirolimus.
 
Pazopanib: Discontinue pazopanib.

Other Adverse Reactions	Other Adverse Reactions	Grade 3	Withhold treatment until Grade ≤ 1, then restart at the same dose level. If recurs, restart at 1 dose level lower.

		Grade 4	Permanently discontinue nab-Sirolimus.
--	--	---------	----------------------------------------

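### Section 6.2.1 and Table 10 give different pazopanib rules for non-refractory Grade 3/4 diarrhea; separately, Table 11's row for other Grade 3 events lacks a drug label

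*Combined protocol and SAP*

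**What the plan says.** **Diarrhea.** Section 6.2.1 sets a residual rule for pazopanib. It opens "For all other Grade 3 or 4 non-hematologic toxicities (except alopecia, nausea, or vomiting" and, for events at least partly attributable to the drug, requires a hold until Grade 1 or better. It continues: "Treatment should then be resumed at a reduction of one dose level". Diarrhea is not among the exceptions. Table 10 (Section 6.2.2) has its own residual row for Grade 3 or 4 non-hematologic events, also with a hold and a one-level reduction. That row leaves out nausea, vomiting and diarrhea unless they resist antiemetic or antidiarrheal treatment.

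**Other Grade 3 events.** Table 11 (Section 6.5) is titled for events possibly related to both drugs. Its Grade 3 row for other adverse reactions tells the reader to withhold treatment until Grade 1 or better, "then restart at the same dose level. If recurs, restart at 1 dose level lower". No drug is named. The Grade 4 row beneath it reads "Permanently discontinue nab-Sirolimus". Section 6.2.1 states: "For pazopanib dose reduction and stopping rules, please refer to Table 10 and Table 11".

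**Surrounding rules.** Pazopanib moves in 200 mg steps, and "Subjects requiring a dose reduction below 200 mg daily should discontinue pazopanib therapy". If toxicity abates, "the study drug dose can then be increased step-wise back to the pre-event dose", after 14 days of monitoring at each level. Section 6.2.2 says pazopanib changes should follow Table 10, and adds that "Additional dose reductions may be made outside of the defined parameters below, at" the investigator's discretion.

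**The concern.** These are default instructions after severe toxicity. For the same non-refractory Grade 3/4 diarrhea, a prescriber working from 6.2.1 halves the dose from 400 mg, while one working from Table 10 need change nothing. Either action can be recorded as a departure from the other rule.

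The Table 11 row raises a similar but smaller problem. A prescriber sent there by 6.2.1 finds an instruction with no drug label, and its restart dose is not the one that Table 10 and 6.2.1 give for pazopanib.

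Dose modification has been frequent in this combination. Section 2.3 reports that 11 of the first 13 subjects had one or both drugs reduced, although those cohorts started pazopanib at 800 mg with Day 1 and Day 8 dosing.

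**Working it through.** The plan states no figure to reproduce. The check sets the rules side by side and follows the dose through them.

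**Inputs.** Pazopanib start 400 mg (all Day 1 only cohorts, Tables 2 and 8); step 200 mg and floor 200 mg (6.2.1).

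**Main point: non-refractory Grade 3/4 diarrhea**

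| Current pazopanib dose | Section 6.2.1 | Table 10 |
|---|---|---|
| 400 mg | hold, resume at 400 − 200 = 200 mg | no required change: 400 mg |
| 200 mg | 200 − 200 = 0, below the floor: discontinue | no required change: 200 mg |

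The difference is 200 mg/day in both rows. In the second row it decides whether the subject stays on pazopanib.

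The two texts cannot both have full effect. If 6.2.1 governs, diarrhea is always held and reduced, and Table 10's refractory condition does nothing for diarrhea. If Table 10 governs, the absence of diarrhea from the 6.2.1 exceptions does nothing. No other row settles it for pazopanib: Table 10 has no diarrhea row, and Table 9's diarrhea row covers nab-Sirolimus only.

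**Lesser point: other Grade 3 events, with Table 11 read literally for pazopanib**

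| Event, starting at 400 mg | Table 11 as written | Section 6.2.1 (same first step in Table 10) |
|---|---|---|
| First | 400 mg | 400 − 200 = 200 mg |
| Recurrence, dose not re-escalated under 6.2.1 | 400 − 200 = 200 mg | 200 − 200 = 0, below the floor: discontinue |
| Recurrence, after re-escalation to 400 mg under 6.2.1 | 400 − 200 = 200 mg | 400 − 200 = 200 mg |

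The firm difference is the one after the first event, 400 against 200 mg. At recurrence the rules differ only if the dose was not re-escalated.

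**Scope of the lesser point.** Table 10 and 6.2.1 cover only non-hematologic toxicity in their residual rules, and Table 11 covers only events possibly related to both drugs. The overlap is therefore non-hematologic, attributable to both drugs, and without a row of its own.

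**The case against.** **On diarrhea.** Just before its residual rule, 6.2.1 sends specific toxicities to Section 6.2.2, and 6.2.2 says to follow Table 10. Since Table 10 mentions diarrhea expressly, the specific clause could be said to prevail. That is a reasonable reading and probably the intended one. It does not close the matter, because Table 10 gives diarrhea no algorithm. It names diarrhea only to exclude it from its own residual row, and no statement of precedence removes it from the rule in 6.2.1.

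**On Table 11.** The case that the row concerns nab-Sirolimus alone is strong. Its restart wording repeats the corresponding Table 9 row, its Grade 4 companion names only nab-Sirolimus, and the hematologic and hepatic rows of Table 11 label pazopanib instructions as such. Section 6.4 also sends nab-Sirolimus dosing to Tables 9 and 11. A reader might infer that the protocol directs full-dose pazopanib after a Grade 3 event. The documents do not support that; what stands is a missing label in a table that 6.2.1 cites for pazopanib. If the row were nevertheless applied to pazopanib, it could also catch Grade 3 diarrhea related to both drugs and give a third answer: hold, then restart at the same dose.

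**On consequence.** The discretion in 6.2.2 to reduce further applies to both points, so the lower dose is always open. It does not decide which action is the default.

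**On nausea and vomiting.** A reader might count refractory nausea or vomiting as another conflict, since 6.2.1 exempts them outright. It need not be one: 6.2.1 only leaves them out of its residual rule, and Table 10 supplies the rule for refractory cases.

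**Conclusion.** The concern holds as a minor inconsistency in dosing text. The two pazopanib rules for non-refractory Grade 3/4 diarrhea disagree: 200 against 400 mg for a subject at 400 mg, and discontinuation against no change for a subject at 200 mg. The text leans toward Table 10 without settling it. The Table 11 point is a labelling omission of narrower scope, worth 400 against 200 mg after a first event if the row is read literally.

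The sizes assume the current 400 mg start, the 200 mg step and floor, and no use of the discretion to reduce further.

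Three larger inferences are not supported:

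- **Frequency.** Section 1.3 gives diarrhea in 58% on pazopanib against 16% on placebo in the phase 3 trial, but without grade. The documents do not give the rate of Grade 3/4 diarrhea, or of other Grade 3 events, at 400 mg with Day 1 dosing.
- **Operating characteristics.** Neither rule enters the phase 2 error rates or sample size, so no design figure changes.
- **Between-site variation.** Section 5.1 names one site, so the documents show no such effect.

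**What to change.** 1. Use one exception list in 6.2.1 and in Table 10's residual row: Table 10's list with its refractory condition, plus alopecia, which 6.2.1 already exempts. This fits Table 9, where the nab-Sirolimus diarrhea rule also applies only when optimal medication has failed. It also removes any doubt about refractory nausea and vomiting.
2. In Table 11, label the Grade 3 row for other adverse reactions 'Nab-Sirolimus', and add 'Pazopanib: see Table 10' for non-hematologic events.

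The cost is negligible: amendment wording in 6.2.1, Table 10 and Table 11, with no new data, visits or subjects.

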## **6.6. Overdose**

### **6.6.1. Nab-Sirolimus**

On a per dose basis, an overdose is defined as 10% over the protocol-specified dose of nab-Sirolimus or pazopanib assigned to a given subject, regardless of any associated AEs or sequelae.

On a schedule or frequency basis, an overdose is defined as anything more frequent than the protocol required schedule or frequency.

On an infusion rate basis, an overdose is defined as any rate faster than the protocol-specified rate of 30 minutes (+10 minutes) for each infusion.

### **6.6.2. Pazopanib**

No MTD was reached in the dose escalation study of pazopanib administered as a single agent at repeated doses of up to 2000 mg/day (Study VEG10003). Systemic exposure to pazopanib at steady-state appeared to plateau at doses greater than 800 mg once daily. Increases in the daily pazopanib dose above 800 mg in the fasted state resulted in a small or no increase in mean systemic exposure to pazopanib.

## **7. STUDY DRUG MANAGEMENT**

### **7.1. Description of Study Drugs**

#### **7.1.1. Nab-Sirolimus Packaging, Labeling, and Storage**

Nab-Sirolimus will be supplied Aadi Bioscience in single-use vials as lyophilized product. Each single-use 50-mL vial will contain 100 mg rapamycin and approximately 800 mg of human albumin as a stabilizer. Each vial will be labeled according to country-specific regulatory requirements for labeling of IPs.

Unopened vials of nab-Sirolimus should be stored in a refrigerator (2°-8°C; 36°-46°F) in original cartons to protect from light. Reconstituted nab-Sirolimus may be stored for up to 4 hours at 2-8°C (36°- 46°F), followed by 4 hours at room temperature (<25°C) in the IV bag. Both unopened vials of nab-Sirolimus and reconstituted nab-Sirolimus should be stored in an area free of environmental extremes and must be accessible only to study personnel.

Temperature records for nab-Sirolimus must be made available to Aadi Bioscience or Sponsor-Investigator approved monitoring teams for verification of proper study drug storage.

### **7.2. Nab-Sirolimus and Pazopanib Accountability, Disposal, and Compliance**

#### **7.2.1. Nab-Sirolimus**

For nab-Sirolimus, only completely unused study drug vials should be retained by the site until a representative from Aadi Bioscience or Sponsor-Investigator approved study monitor has completed an inventory. Partially used and completely used vials should be destroyed according to the site's guidelines, and their disposition should be recorded on the Investigational Drug Accountability Record Form.

For nab-Sirolimus the Sponsor-Investigator, or designee, shall record the dispensing of study drug to subjects and any remaining study drug after dosing in a study drug accountability record. The study drug record will be made available to monitoring personnel for the purpose of accounting for the study drug supply. Inspections of the study drug supply for inventory purposes and assurance of proper storage will be conducted as necessary. Any significant discrepancy will be recorded and reported to the Sponsor-Investigator and Aadi Bioscience or their designee and a plan for resolution will be documented.

Accurate recording of all nab-Sirolimus administration will be made in the appropriate section of the subject's CRF and source documents. The Sponsor-Investigator or designee is responsible for accounting for all study-specific IP either administered or in their custody during the course of the study.

#### **7.2.2. Pazopanib**

Pazopanib is managed as a prescribed medication and administered as standard of care, according to institutional practices.

Accurate recording of all pazopanib administration will be made in the appropriate section of the subject's CRF and source documents. Subjects will complete a daily drug diary recording time of self-administration of pazopanib dosing. This diary will be reviewed at Day 1 of each cycle. Pharmacy accountability and dispensation records will not be maintained for pazopanib.

**7.3. Nab-Sirolimus Reconstitution and Use**

It is not a requirement to use filter needles in the preparation, or in-line filters during the administration of nab-Sirolimus. In any event, filters of pore size less than 15 microns (15  $\mu\text{m}$ ) must not be used.

Nab-Sirolimus will be reconstituted by appropriate study personnel following the Pharmacy Manual and administered to the subject at the study site. The investigator or qualified designee will calculate the BSA of the subject in order to determine the total amount of nab-Sirolimus to be administered.

**7.4. Receipt and Return of nab-Sirolimus**

The process for handling the receipt and return of the study drug supplies are described in the Pharmacy Manual.

## **8. CONCOMITANT MEDICATIONS AND PROCEDURES**

All concomitant treatments, including blood and blood products, must be reported on the CRF. Throughout the study, investigators may prescribe any concomitant medications or treatments deemed necessary to provide adequate supportive care except for those listed in Section 8.2.

Concomitant therapies are to be collected from 28 days prior to signing of informed consent through the 30-Day Follow Up Visit. Therapy name including indication, dose, frequency, route, start date and stop date will be recorded on each subject's CRF(s).

### **8.1. Permitted Medications and Procedures**

The investigator must be informed as soon as possible about any medication taken from the time of screening until the end of the clinical phase of the study (final study visit). Any concomitant medication(s), including herbal preparations, taken during the study will be recorded in the CRF. The minimum requirement is that drug name, dose, and the dates of administration are to be recorded. Additionally, a complete list of all prior cancer therapies will be recorded in the CRF.

Subjects should receive full supportive care during the study, including transfusions of blood and blood products, and treatment with antibiotics, anti-emetics, anti-diarrheas, and analgesics, and other care as deemed appropriate, in accordance with their institutional guidelines. WBC growth factors may be administered at the discretion of the investigator, consistent with institutional guidelines.

Extreme precaution must be taken with contraceptives (either combined or progesterone only), as it is not known if there is the potential of inhibition/induction of enzymes that affect the metabolism of estrogens and/or progestins.

### **8.2. Prohibited Medications and Procedures**

The use of certain medications and illicit drugs within 5 half-lives or 28 days, whichever is shorter, prior to the first dose of study drug and for the duration of the study will not be allowed. If a prohibited medication is required for single use (such as for a procedure) while study drug is held, the Sponsor-Investigator can approve such use.

The following medications or non-drug therapies are prohibited:

- Other anti-cancer therapy while on treatment in this study.
- Antiretroviral drugs (subjects with known HIV are ineligible for study participation).
- Herbal remedies (e.g., St. John's wort) unless approval is granted by the Sponsor-Investigator.
- Rapamycin is metabolized primarily by CYP3A4. Drugs that are strong inhibitors or inducers of CYP3A4 may only be used under special circumstances (e.g., as a single use for a procedure) while treatment with study drug is interrupted. The list may be modified based on emerging data.
- Use of any known CYP3A4 substrates with narrow therapeutic window (such as fentanyl, alfentanil, astemizole, cisapride, dihydroergotamine, pimozide, quinidine, terfanide)

within the 14 days prior to receiving the first dose of ABI-009. Other medications may be allowed with approval of the Sponsor-Investigator.

- Use of strong inhibitors and inducers of CYP3A4 within the 14 days prior to receiving the first dose of ABI-009.

## 9. STATISTICAL CONSIDERATIONS

### 9.1. Study Endpoints

#### Endpoints in Phase 1

##### **Primary Endpoint**

- DLT, as defined in Section 6.4.

##### **Secondary Endpoint**

- Adverse Events profile (based on NCI CTCAE v5.0) of all subjects and each dose cohort

#### **Endpoints in Phase 2 – Data from both phase 1 and 2**

##### **Primary Endpoint**

- Progression-free survival (PFS) rate at 3 months, based on Response Evaluation Criteria in Solid Tumors (RECIST) v1.1

##### **Secondary Endpoints**

- Adverse Events profile (based on NCI CTCAE v5.0)
- Median PFS, PFS rate at 6 months, based on RECIST v1.1
- Median OS, OS at 12 months
- Objective response rate (ORR) based on RECIST v1.1
- Disease control rate, defined as CR plus PR plus SD  $\geq 18$  weeks, based on RECIST v1.1
- Duration of response

##### **Exploratory endpoints**

- Correlation of baseline immune parameters with clinical benefit
- Correlation of genetic profiling and optional tissue biomarker analysis with clinical benefit
- Correlation of baseline SPARC expression with clinical benefit

### 9.2. Safety Analysis

The safety analysis set includes all treated subjects.

Safety and tolerability will be monitored through continuous reporting of treatment emergent and TRAEs, AEs of special interest, laboratory abnormalities, and incidence of subjects experiencing dose modifications, dose delay/dose not given, dose interruptions, and/or premature discontinuation of IP due to an AE. All AEs will be recorded by the investigator from the time the subject signs informed consent until 30 days after the last dose of protocol therapy. Adverse events will be graded by NCI CTCAE v5.0.

Physical examination, vital signs, laboratory assessments (e.g., serum chemistry, hematology), and ECOG performance status will be monitored and reviewed per institutional standards. All SAEs (regardless of relationship to IP) will be followed until resolution. Local laboratory analysis will be performed as per study schedule.

### **9.3. Efficacy Analysis**

Subjects will be evaluated for ORR, DCR, or progressive disease (PD) by CT imaging. Contrast enhanced MRI can also be used if CT is contra-indicated, as long as the same modality is used throughout the study. Baseline scan results can be accepted from outside institutions but must be done within 4 weeks of starting therapy and must include (as clinically indicated), chest abdominal, and pelvic CT or MRI. The first response assessment by CT or MRI scans documenting target lesions will be done 6 weeks after C1D1 and should be repeated every 6 weeks for the first year, then every 12 weeks thereafter until the end of treatment. If an initial observation of objective response (CR or PR) is made, a confirmation scan should be done at 6 weeks after initial observation. Scans should continue on schedule regardless of delays in nab-Sirolimus dosing.

The efficacy endpoints of ORR (CR + PR), DCR (CR, PR, and SD  $\geq 18$  weeks), and PFS will be determined by a local radiologic assessment using RECIST v1.1. After the 30-Day Follow Up Visit, subjects will be followed for survival every 12 weeks ( $\pm 3$  weeks), or more frequently as needed, until death, withdrawal of consent, or the study closes, whichever is the earliest.

The number and percentage of subjects achieving response ORR, DCR, or progressed will be summarized.

Median PFS and OS will be summarized using Kaplan-Meier (KM) analysis. Analysis of other efficacy endpoints, PFS rate at 3 and 6 months, and OS rate at 12 months will be assessed via descriptive statistics, for the number of subjects is expected to be small.

Response duration usually will be measured from the time of initial response until documented tumor progression.

### **9.4. Exploratory Analysis**

Presence/level of expression of immune parameters, gene profiling, and SPARC will be analyzed and their relationship to clinical responsiveness will be explored.

### **9.5. Sample Size Considerations**

**Phase 1:** Up to 49 subjects to identify the MTD, but the MTD may be reached with as few as 22 subjects. Subjects who discontinue from the study prior to completing the DLT assessment window for reasons other than toxicity will be replaced at the same dose level.

**Phase 2:** For sample size determination, we assume the following:

1. For aa-TKI/pazopanib monotherapy in nonadipocytic STS, the baseline anticipated PFS rate at 3 months is approximately 50%.
2. An increase by the combination therapy of the PFS rate at 3 months to 70% would be considered clinically meaningful.
3. This is an exploratory phase 1/2 study. Thus, type I (false positive) errors are less worrisome than type II (false negative). We therefore set alpha=0.1 for rejection of null hypothesis. Beta is set at 0.1 (90% power), again, to minimize type II errors.
4. We are using a Simon's two-stage study design for the phase 2 efficacy evaluation.

In the first stage, at least 23 subjects would be enrolled, including the 3-6 subjects from phase 1 at the RP2D. If at least 11 were progression-free at the 3 months evaluation, then additional subjects would be enrolled to a total of 39 subjects in Phase 2. If at least 23 were progression-free at 3 months, then this would provide preliminary data to indicate that the combination was active and worthy of further evaluation in this clinical setting.

Subjects who fail to become evaluable for the secondary endpoint with a follow-up CT/MRI will be replaced.

To assess the primary endpoint, we elected to use a Simon's minimax design. This was selected to be most conservative in evaluable subjects needed to answer the primary hypothesis. In this case, a total of 39 evaluable subjects will be required in the phase II component of the study, if it extends through both stages.

This type of design has greater statistical power than a single-arm design. For example, a single arm trial enrolling the same number of subjects (n=39) would only have a statistical power of 82%, versus 90% for the proposed design. Alternatively, it would require 50 evaluable subjects in a single-arm design to achieve the desired 90% power.

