### **3. STUDY POPULATION**

#### **3.1. Number of Subjects**

**Phase 1:** up to 49 subjects to identify the MTD, but the MTD may be reached with as few as 22 subjects. Subjects who discontinue from the study prior to completing the DLT assessment window for reasons other than toxicity will be replaced at the same dose level.

**Phase 2:** In the first stage, at least 23 subjects would be enrolled, including the 3-6 subjects from phase 1 at the RP2D. If at least 11 were progression-free at the 3 months evaluation, then additional subjects would be enrolled to a total of 39 subjects in the Phase 2.

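### Both phase 2 cut-offs are one below the minimax design's; as written, the rule has a nominal false-positive rate of 16.7%, not 10%

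*Combined protocol and SAP*

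**What the plan says.** Section 9.5 (Sample Size Considerations) takes a 3-month PFS rate of about 50% for anti-angiogenic TKI or pazopanib monotherapy as the null, and 70% as the rate worth detecting. On error rates it says "We therefore set alpha=0.1 for rejection of null hypothesis", and it sets beta at 0.1 for 90% power. For the type of design it says "we elected to use a Simon's minimax design".

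Stage 1 has at least 23 subjects, including the 3 to 6 treated at the RP2D in phase 1. The interim rule is: "If at least 11 were progression-free at the 3 months evaluation, then additional subjects would be enrolled to a total of 39 subjects". The final rule begins: "If at least 23 were progression-free at 3 months, then this would provide preliminary data", and the sentence goes on to treat that count as showing an active combination worth further study.

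Section 3.1 (Number of Subjects) repeats the interim rule: "If at least 11 were progression-free at the 3 months evaluation". Neither section, nor any other part of the document, expresses either limit as a count to be exceeded.

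**The concern.** Simon designs are usually written as r1/n1 and r/n, where r1 and r are the largest counts that still lead to stopping or to failure to reject. The protocol's 11 and 23 are exactly those values for its stated inputs, yet the text treats them as the smallest counts that pass. Each threshold is therefore one too low.

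These are the only efficacy decision thresholds for phase 2. If the final one is too low, the trial can call the combination active at a false-positive rate above the one it set. If the interim one is too low, the trial continues at 11/23 = 47.8%, which is below its own 50% null, and up to 39 − 23 = 16 further subjects are enrolled on a result that the named design treats as futile.

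**Working it through.** **Inputs (Section 9.5).** p0 = 0.50, p1 = 0.70, alpha = 0.10, beta = 0.10, minimax, n1 = 23, n = 39. Alpha is taken as one-sided, as is standard for a Simon design.

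**Formula.** Let a1 be the smallest stage 1 count that continues and a the smallest total that counts as success. With X1 ~ Bin(n1, p) and X2 ~ Bin(n − n1, p) independent:

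P(success | p) = Σ over x from a1 to n1 of P(X1 = x) · P(X2 ≥ a − x)

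Type I error is this sum at p = 0.50, and power is the sum at p = 0.70. The probability of early termination under the null is PET = P(X1 ≤ a1 − 1 | 0.50). The expected size is E(N) = n1 + (1 − PET)(n − n1).

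**Step 1: reproduce the plan's sample size.** An exhaustive search requiring alpha ≤ 0.10 and power ≥ 0.90 finds no design for n = 34 to 38. At n = 39, the design with the smallest expected size under the null has n1 = 23, r1 = 11 and r = 23: stop at 11 or fewer, and do not reject at 23 or fewer. The plan's 23 and 39 are therefore reproduced, and the intended design is identified. In passing-count form it is a1 = 12, a = 24.

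**Step 2: evaluate the written rule, the design's rule, and each single correction.**

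| Continue at | Success at | Type I error | Power | PET under null | E(N) under null |
|---|---|---|---|---|---|
| ≥11 of 23 (as written) | ≥23 of 39 (as written) | 0.1667 | 0.9486 | 0.339 | 33.6 |
| ≥12 of 23 | ≥23 of 39 | 0.1605 | 0.9422 | 0.500 | 31.0 |
| ≥11 of 23 | ≥24 of 39 | 0.0995 | 0.9050 | 0.339 | 33.6 |
| ≥12 of 23 (minimax) | ≥24 of 39 (minimax) | 0.0978 | 0.9015 | 0.500 | 31.0 |

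Expected sizes: 23 + (1 − 0.339) × 16 = 33.6, and 23 + 0.5 × 16 = 31.0.

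The final cut-off drives the alpha excess. Correcting it alone gives 0.0995, while correcting only the interim cut-off leaves 0.1605. The interim cut-off governs futility: as written, a null regimen passes stage 1 with probability 1 − 0.339 = 0.661 rather than 0.50.

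**Step 3: cross-check at the boundary.** Ignoring the interim look, the exact one-sided 90% lower bound is 0.474 for 23/39 and 0.5001 for 24/39. Only the latter excludes 0.50. The plan does not call for this interval; it is used here only as a check.

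**Step 4: stage 1 size.** All figures above assume the interim decision uses exactly 23 subjects. The text sets 23 as a minimum but fixes the count of 11. As an illustration only (the plan gives no larger number), with 26 subjects in stage 1 and the cut-off still at 11, P(Bin(26, 0.5) ≥ 11) = 0.84, so a null regimen would continue 84% of the time.

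**The case against.** The strongest defence concerns consequence. The study calls itself exploratory, says false positives worry it less than false negatives, treats success as preliminary data, and in Section 9.3 describes the 3-month PFS rate as a descriptive analysis. The error is lenient and costs no power. This limits the harm, but Section 9.5 uses the same argument to choose alpha = 0.10, and the written rule exceeds that already relaxed limit.

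Other readings do not rescue the rule:

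- **Interim look treated as non-binding.** A single-stage rule of at least 23 of 39 still has type I error 0.168.
- **Alpha meant as two-sided.** That implies 0.05 in the relevant direction, so the excess would be larger.

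Several points of scope do stand. The interim cut-off contributes almost nothing to the alpha excess, and keeping it at 11 with success at 24 would meet both stated error rates, though that is not the minimax design with the smallest expected size. The minimum of 23 in stage 1 may be only an enrolment allowance to reach 23 evaluable subjects, since Section 9.5 provides for replacing subjects without a follow-up scan. These are the phase 2 efficacy thresholds, not the trial's only decision rules: Section 2.3 has the 3+3 rules for phase 1. How the slip arose is an inference from the matching numbers.

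**Conclusion.** The concern holds. For the inputs in Section 9.5, both written cut-offs are one below those of the design the protocol names. The rule as written has type I error 0.167 against the stated 0.10. Its power is 0.949, and its probability of stopping early under the null is 0.34 instead of 0.50. The final cut-off accounts for nearly all of the alpha excess. The interim cut-off is a lesser, separate fault that raises the expected size under the null from 31.0 to 33.6.

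These are nominal binomial figures. They assume 23 subjects at the interim look, 39 in total, and independent outcomes in subjects not selected on outcome. Counting the phase 1 RP2D subjects, when Section 2.3 bases the RP2D partly on efficacy, and replacing subjects who lack a follow-up scan both put some strain on the last assumption. Neither changes the finding that the cut-offs disagree with the stated design. The correction is needed before the counts are known, because a result of exactly 11/23 or 23/39 would otherwise be open to dispute.

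**What to change.** - **Sections 9.5 and 3.1, interim rule:** continue to stage 2 only if at least 12 of the first 23 evaluable subjects are progression-free at 3 months; stop if 11 or fewer are. State that this decision rests on exactly those 23 subjects, even if more have been enrolled.
- **Section 9.5, final rule:** declare the combination active only if at least 24 of 39 evaluable subjects are progression-free at 3 months.
- **Section 9.5, operating characteristics:** report one-sided nominal alpha 0.098, nominal power 0.902, probability of early termination under the null 0.50, and expected size under the null 31.0.

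The cost is wording in two sections. No extra subjects are needed. Power falls from the 0.949 of the written rule to 0.902, which still meets the stated 90%.
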